Specific Aim 1: Test the hypothesis that clopidogrel monotherapy is safe following successful PCI among 100 consecutive patients with HBR and meeting the inclusion criteria (100 *active* patients, excluding patients who have been enrolled then withdrawn for various reasons such as starting an additional blood thinner, patient preference, etc.). To ensure that we have data on 100 active patients that complete their 1 month visit, we will plan to accrue up to 150 patients. The primary safety end point will be showing noninferiority of clopidogrel monotherapy in reducing ischemic events stratified by presence or absence of *CYP2C19* LOF allele (QuantStudio with Chemagic DNA extraction). All patients will receive clopidogrel (600 mg load & 75 mg maintenance) and aspirin (324 mg load & 81 mg maintenance) for the first week. Those with *CYP2C19* 2* or 3* LOF allele (*CYP2C19* LOF carriers) will be prescribed prasugrel or ticagrelor [prasugrel 60 mg load, maintenance 10 mg or 5 mg (for patients \geq 75 years or $<$ 60 kg) daily or ticagrelor 180 mg load, maintenance 90 mg twice daily (dose escalation with bolus will occur regardless of the timing of the last clopidogrel dose)]. Non-carriers (or those with inconclusive results) will continue with clopidogrel 75 mg daily maintenance dose. Aspirin will be stopped in all patients once *CYP2C19* results are available.

Specific Aim 2: Among participants enrolled in aim 1, aim 2 will determine the incidence of BARC 3 or 5 bleeding events. Other secondary endpoints are post-dismissal all-cause death, any MI up to 180 days, repeat revascularization, or any other BARC bleeding episodes.

SIGNIFICANCE

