- Design Overview.** For *Aim 1*, up to 150 participants with HBR on DAPT with clopidogrel and aspirin, who have undergone successful PCI will be stratified by the *CYP2C19* LOF allele within one week of DAPT initiation. If present, participants will be given prasugrel or ticagrelor monotherapy, and non-carriers will continue with clopidogrel monotherapy. The primary safety endpoint will be a composite of post-dismissal cardiac death/spontaneous MI <30 days or stent thrombosis <90 days of discharge. For *Aim 2*, the same subjects will undergo post-dismissal assessment for BARC 3 or 5 bleeding, all-cause death, any MI, and/or repeat revascularization up to 180 days. Informed consent followed by genotype assessment will be obtained prior to discharge. Loading dose of clopidogrel (600 mg) will be given to all patients and maintenance dose of 75 mg daily will be given, as indicated. We will allow patients to be given loading dose (324 mg) of aspirin either before or at the time of PCI. The choice of stents, access site and treatment site will be at the discretion of the treating physician (**Figure 1**).
- Clopidogrel and prasugrel/ticagrelor administration.** This study will be single-center, single-arm, open label, first-in-human, and a proof-of-concept, pilot and safety study. All participants in the first week will receive clopidogrel bolus (600 mg) and maintenance (75 mg) and aspirin bolus (324 mg, if not on aspirin) and 81mg maintenance. Participants with HBR who meet the inclusion criteria will be stratified by *CYP2C19* LOF allele. Non-carriers (or those with inconclusive results) will continue with maintenance dose of clopidogrel monotherapy at 75 mg daily. If LOF allele is present, they will be prescribed either prasugrel or ticagrelor monotherapy [prasugrel 60 mg load, maintenance 10 mg daily; ticagrelor 180 mg load, maintenance 90 mg twice daily; dose escalation with bolus regardless of timing of the last clopidogrel dose]. Prasugrel will be the preferred agent except when absolutely contraindicated (history of stroke/transient ischemic attack or active bleeding). Patients ≥ 75 years or < 60 kg will receive prasugrel at a reduced dose of 5 mg daily. If there is

Figure 1: Study Flow Chart

a relative contraindication to prasugrel (as determined by the treating physician), the participant will be given ticagrelor. Maintenance aspirin will be discontinued in both arms once genotype testing has been confirmed. (**Figure 1**).

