 - c) **Subject Accrual Plan:** The recruitment will be drawn from the Earl Wood Cardiac Catheterization Laboratory (>1,500 PCIs/year) and Cardiology inpatient services at St. Mary's Hospital. Day 1 will include screening following successful PCI, bleeding risk calculation (ARC-HBR), enrollment, informed consent, and clinical CYP2C19 assay collection. On day 30, a study coordinator phone call will occur to assess ischemic symptoms, readmission, and bleeding. On day 90, a study coordinator phone call will again assess ischemic symptoms, readmissions, and bleeding. All encounters will include drug education and assurance of compliance.
 - d) **Reassessment:** The study coordinator will make phone calls at one and three months to inquire about ischemic symptoms, readmissions at other hospitals with MI, or any bleeding.
7. **Control Cohort:** A cohort of similar patients will be identified from the Mayo Clinic catheterization laboratory PCI registry to determine rates of ischemic and bleeding events in a cohort of HBR post-PCI patients receiving standard of care DAPT after PCI. These patients will be identified by registry review, and we will utilize ICD diagnosis codes to identify bleeding and ischemic events. Retrospective chart review will verify the clinical situation to ensure the validity of the coded diagnoses (to minimize errors inherent to diagnosis coding). There will be no direct patient contact, and patients who refused registry research participation will be excluded from this study. We aim to obtain the following

data:

A. Events

- Event type (category below); diagnosis codes selected from Mayo Clinic database of ICD codes (<https://intranet.mayo.edu/charlie/quantitative-health-sciences-groups/rochester-epidemiology-project/index-of-possible-codes-for-specific-conditions-diseases/>)
- Date of ischemic/bleeding event
- Bleeding Categories
 - *Hemorrhage, gastrointestinal*
 - *Stroke (hemorrhagic)*
 - *Disease, cerebrovascular (hemorrhagic)*
 - *Hematuria*
- Ischemic Categories
 - *Infarction, myocardial*
 - *Disease, cerebrovascular (TIA, ischemic stroke)*

B. Inclusion

- Successful PCI
- Approx. 1 year date range TBD (n = 1500 patients; targeting contemporary PCI patients within the last 2 years).

C. Exclusion

- Enrolled in CHAMP Trial

D. Demographic/Procedure Info to Capture from PCI Registry

- Age/DOB
- Sex
- Race
- Event type (STEMI, NSTEMI/unstable angina, chronic CAD)
- PCI date
- Hemoglobin at time of PCI

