Introduction. PDB is common and is seen in approximately 5% and 20% of those bleeds manifest in the first month following PCI. Longer observation is needed to accurately define its incidence, source, severity, and time dependency. The ischemic hazard usually follows admission due to PDB and is likely due to interruption or discontinuation of DAPT. Insights into its time course, relationship with antecedent bleeding, type of MI (STEMI vs. NSTEMI) and prognosis are equally relevant.

Prolongation of observation is critical to delineate time course of both bleeding and ischemic hazards. The objectives of Aim 2 are to determine the frequency, time course, type, severity, and prognosis of both ischemic and bleeding events till the end of 6 months. The working hypothesis is that most PDB and ischemic events occur early after PCI, however, increase in both ischemia and bleeding may continue, especially among participants with ACS. We further hypothesize that participants receiving clopidogrel monotherapy will continue to demonstrate lower incidence of bleeding as compared to the standard of care with DAPT. Our approach to test this hypothesis will be to do extended period of observation till 6 months and record both bleeding and ischemic events. The rationale for this aim is that the main driver for increase in PDB and consequent ischemia is the intensity and duration of DAPT, however most bleeds and ischemia occur early, questioning the need to extend the duration of DAPT. After successful completion of the proposed studies for Aim 2, it is our expectation that using a prospective design, we will have identified predictors of PDB and ischemia.

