Preliminary Studies. Research Design: Same 150 participants from Aim 1 will be enrolled, however, data for Aim 2 will be collected at six months. Our main strategy for this aim is to demonstrate whether clopidogrel monotherapy, guided by genotype, is associated with lower bleeding and ischemic events during extended period of observation, especially relevant in participants presenting with ACS. **Expected Outcomes:** Upon completion, we will have comprehensive data on incidence, severity, predictors, type, and time trends for both PDB and ischemia. In recent years, several trials have analyzed PCI in HBR patients examining DAPT regimens and outcomes to balance the risk of ischemia and bleeding. **Table 3** (see supplemental material) summarizes these key trials. Extending the period of observation allows us to monitor the participants longer and demonstrate the safety of clopidogrel monotherapy. From this aim we will determine whether clopidogrel monotherapy is safe in all-comers following successful PCI, especially among participants presenting with ACS, as the current guidelines recommend at least 6 months of DAPT. Importantly, with this aim, we will focus on the period between 3 and 6 months for both ischemic and bleeding events. The idea is that by providing early deescalation with a P2Y12 inhibitor, clopidogrel will lead to lowering in the incidence of PDB. The observation period will continue even beyond 6 months as all participants will be entered into the Mayo Clinic database. We expect that subjects receiving clopidogrel monotherapy will have reduced PDB during 6 months of observation. If the data confirm our hypotheses, we will expect our hypothesis and will have shown after completion of Aim 2 that clopidogrel monotherapy is safe and effective during 6 months of observation.

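### The available text specifies no adjustment for comparing trial participants with registry controls on DAPT, although the main case-mix variables are already listed for controls

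*Combined protocol and SAP*

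**What the plan says.** General Methods describes the design: "This study will be single-center, single-arm, open label, first-in-human, and a proof-of-concept, pilot and safety study". There is no concurrent DAPT group.

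Section 7 (Control Cohort) supplies the external one: "A cohort of similar patients will be identified from the Mayo Clinic catheterization laboratory PCI registry to determine rates of ischemic and bleeding events", the patients being HBR and on standard DAPT. Its itemized criteria are shorter: successful PCI, a date range of about one year with n = 1500, and not being enrolled in the trial. The fields to capture include age, sex, race, presentation, hemoglobin, creatinine and eGFR, P2Y12 inhibitor and oral anticoagulant use. The text then moves to Aim 1 without saying how the two groups will be compared.

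Two statements under Aim 2 are comparative. The Introduction hypothesizes that "participants receiving clopidogrel monotherapy will continue to demonstrate lower incidence of bleeding as compared to the standard of care with DAPT". The Research Design paragraph gives as the aim's main strategy to show whether genotype-guided clopidogrel monotherapy "is associated with lower bleeding and ischemic events during extended period of observation".

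On control numbers, the Significance section (Proposed Strategy to Reduce Ischemic Hazard) plans as many HBR controls as there are participants, which differs from the 1500 in Section 7.

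**The concern.** The comparison is not randomized, and the two groups are filtered differently. Participants must consent and be judged likely to comply. They are excluded for chronic oral anticoagulation, angiographic thrombus, several lesion and stent features, planned surgery and life expectancy under a year (Section 6). The itemized control criteria contain none of these. Anticoagulant use is recorded for controls but is not an exclusion.

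The listed covariates matter for the outcomes. Age, hemoglobin and eGFR are bleeding criteria in the protocol's Table 1, and the protocol singles out acute coronary syndrome for ischemic concern. If participants and controls differ on them, a crude difference in rates mixes who was enrolled with what the strategy did. A descriptive contrast is confounded in the same way as a tested one.

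**Working it through.** **What there is to reproduce.** The plan gives no expected rate, margin, alpha or power for the registry comparison. Its sizing figures are 100 active patients with accrual up to 150 (Specific Aim 1) and the two control numbers. The laboratory performs more than 1,500 PCIs a year, so 1500 is about one year of all PCIs, before restriction to HBR. The protocol puts the HBR share at about 15% generally and 30% at this site: 1500 × 0.15 = 225 and 1500 × 0.30 = 450 HBR controls before other exclusions. Under the Significance section there would be about 100 to 150.

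**One unbalanced factor, no treatment effect.** For a factor with risk ratio k, present in share p_t of participants and p_c of controls, the crude ratio is [1 + p_t(k − 1)] / [1 + p_c(k − 1)]. All shares and risk ratios here are assumptions; the documents give none.

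- k = 2, 30% vs 50%: 1.30/1.50 = 0.87
- k = 3, 30% vs 50%: 1.60/2.00 = 0.80
- k = 3, 5% vs 20%: 1.10/1.40 = 0.79
- k = 3, 40% vs 30%: 1.80/1.60 = 1.125

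**Entry criteria that differ.** If a share p of controls takes anticoagulants with bleeding risk ratio k, and no participant does, the crude ratio is 1/[1 + p(k − 1)]. For p = 0.10 and k = 1.5 this is 1/1.05 = 0.95; for p = 0.30 and k = 3 it is 1/1.60 = 0.63. If the 1500 were not restricted to HBR, with 30% HBR and risk ratio k for HBR, it is k/(0.3k + 0.7): 1.5/1.15 = 1.30 for k = 1.5 and 3/1.6 = 1.88 for k = 3. The bias can go either way.

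**Several factors, before and after weighting.** A simulation of 1,500 runs with no treatment effect used 100 participants and 450 controls. Assumed shares (participants vs controls) and risk ratios were: older age 50% vs 65%, 1.5; anemia 35% vs 50%, 2; CKD 35% vs 45%, 1.5; ACS 45% vs 60%, 1.3; sex balanced. By hand, the expected crude ratio is (1.25/1.325) × (1.35/1.50) × (1.175/1.225) × (1.135/1.18) = 0.78. The simulation gave 5.64% vs 7.21%, also 0.78. After propensity weighting of controls to the participants, the control rate was 5.64% and the ratio 1.00, with an effective control n of about 314. That is 314/450 = 70%; at the same proportion, 100 to 150 controls would become about 70 to 105. The correction is complete only because every simulated confounder was measured.

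**Why weighting rather than an outcome model.** The Background's 1 in 20 readmitted for bleeding gives about 5 events in 100 participants. Seven parameters (intercept, age, sex, two for presentation, hemoglobin, eGFR) leave 5/7 = 0.7 events each. A propensity model has 100/7 = 14 participants per parameter.

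**Sampling error for scale.** At 5% in both groups with 100 vs 450, the SE of the log ratio is √(1/5 − 1/100 + 1/22.5 − 1/450) = 0.482, so a true ratio of 1 has an approximate 95% interval of exp(±1.96 × 0.482) = 0.39 to 2.57.

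**What weighting cannot reach.** Table 1 lists 20 criteria (14 major, 6 minor). The five variables cover 5 of them (age, two eGFR levels, two hemoglobin levels), and anticoagulant use makes 6. Lesion features are not in the control list. Trial outcomes are adjudicated BARC bleeding, cardiac death, MI and stent thrombosis. Control outcomes are ICD-coded, chart-verified gastrointestinal, intracranial and urinary bleeding, MI, and stroke or TIA, with no category for death or stent thrombosis.

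**The case against.** The strongest reply is that a crude comparison is inferred from silence. No sentence says the rates will be unadjusted, and no test against the registry is described. The text breaks off mid-sentence under Aim 2's potential problems, and references 28 to 34 are cited nowhere in it, so a statistical section may be missing from this copy. A reader might infer that the plan commits to unadjusted rates; the documents do not support that. What stands is narrower: Section 7, where the cohort is defined, names no method and points to none.

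A reader might also infer that any difference will be credited to dropping aspirin. No passage says so. The strategy also assigns the P2Y12 inhibitor by genotype, so a contrast would concern the whole strategy.

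The comparison itself is partly inferred: the Aim 2 hypothesis refers to standard care without naming the registry cohort, and a pilot may intend only a benchmark. That is fair, but no other DAPT group is described, and a benchmark is still confounded. The plan does ask for similar, HBR patients on DAPT, which is a step towards comparability, but its itemized criteria do not carry it out.

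Finally, the assumed single-factor shifts of 0.79 to 1.125 lie well inside the 0.39 to 2.57 interval, and five variables leave most ARC-HBR criteria untouched. Both points hold. They argue for modest claims and a descriptive label, not for leaving measured confounders unused.

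**Conclusion.** The concern holds in a limited form. The available text specifies no adjustment for a non-randomized comparison on which Aim 2's statements about standard DAPT depend, although five relevant variables are listed for controls and should be obtainable for participants, who are to be entered in the institution's database. Followed as written, Section 7 yields a contrast that partly reflects case mix and differing entry criteria.

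The size cannot be fixed from the documents. Under the stated assumptions, case mix alone gives crude ratios from 0.78 to 1.125. The anticoagulant difference gives 0.95 to 0.63, and an unrestricted control group would give 1.30 to 1.88. The direction is not determined, and with about 5 events chance is a larger source of uncertainty than most of these shifts. The adjustment gap is conditional on no method being stated in a part missing from this copy. The conflict over control numbers is in the text itself.

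**What to change.** In Section 7, before control outcomes are examined:

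1. Restrict controls to HBR patients who meet the trial's eligibility rules as far as the data allow, including exclusion of oral anticoagulant users, a field already captured.
2. Report each trial-versus-control contrast with controls weighted to the participants' mix of age, sex, presentation, hemoglobin and eGFR, using propensity weights that target the treated. Show crude rates beside the weighted ones, with the effective control n and confidence intervals. Take the same fields for participants from the same database. Leave the P2Y12 inhibitor out of the weights, since it is part of the strategy compared.
3. Reconcile the control number: 1500 in Section 7 against as many as the participants in the Significance section.
4. Limit contrasts to outcomes defined alike in both groups, and label the comparison descriptive and only partly adjusted, because most ARC-HBR criteria and the lesion features are not in the control data.

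If another section already states an adjustment method, refer to it in Section 7 instead of adding one.

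The cost is a paragraph of protocol text and a small analysis on listed fields. The downside is a smaller effective control sample, which matters most if the Significance section governs and there are only about 100 to 150 controls before weighting.

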| Spontaneous bleeding requiring hospitalization or transfusion in the past 6 months or at any time, if recurrent | Spontaneous bleeding requiring hospitalization or transfusion within the past 12 months not meeting the major criterion |
| Moderate or severe thrombocytopenia (platelet count $<100 \times 10^9/L$) present prior to PCI | |
| Chronic bleeding diathesis | |
| Liver cirrhosis with portal hypertension | |
| Recent major surgery or major trauma within 30 days before PCI | Long-term use of oral nonsteroidal antiinflammatory drugs (NSAIDs) or steroids |
| Active malignancy (excluding nonmelanoma skin cancer) within the past 12 months | |
| Previous spontaneous intracranial hemorrhage (at any time) | Any ischemic stroke at any time not meeting the major criterion |
| Previous traumatic intracranial hemorrhage within the past 12 months | |
| Presence of a bleeding arteriovenous malformation | |
| Moderate or severe ischemic stroke within the past 6 months | |
| Nondearable major surgery on DAPT | |

Table 2: Percent of Patients with Death or Myocardial Infarction After PCI

| Year | 30 days | 60 days | 90 days |
|--------|---------|---------|---------|
| 2010 | 14% | 16% | 17% |
| 2011 | 17% | 20% | 22% |
| 2012 | 10% | 11% | 13% |
| 2013 | 9% | 11% | 13% |
| 2014 | 6% | 8% | 8% |
| 2015 | 6% | 8% | 9% |
| 2016 | 5% | 6% | 7% |
| 2017 | 5% | 6% | 6% |
| Total* | 9% | 11% | 12% |

*MI data unavailable after 2017; Data from Mayo Clinic, Rochester, MI, myocardial infarction

clinical trials, including genotype-directed randomization for the TAILOR PCI trial. We will approach potential participants for informed consent before dismissal following the PCI procedure. For participant with same-day dismissal, we will approach them either before coronary angiography or pre-dismissal once the sedation from the procedure wears off.

Aim 2: Detailed Approach

Aim 2 includes participants enrolled in Aim 1, and this data will determine the incidence of post-discharge BARC 3 or 5 bleeding events. Other secondary endpoints are post-dismissal all-cause death, any MI up to 180 days, repeat revascularization, or any other BARC bleeding episodes. The rate of death or MI post-PCI at Mayo Clinic, Rochester is presented in **Table 2**.

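### The trial and its registry controls count different ischemic events, with stroke/TIA on the control side only and death, stent thrombosis and revascularization on the trial side only, so the rates are not comparable.

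*Combined protocol and SAP*

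**What the plan says.** All references are to the combined protocol and SAP.

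- **Control cohort (General Methods, item 7, A. Events).** Its purpose is "to determine rates of ischemic and bleeding events in a cohort of HBR post-PCI patients receiving standard of care DAPT after PCI". There are two ischemic categories: "Infarction, myocardial" and "Disease, cerebrovascular (TIA, ischemic stroke". Events are recorded by type and date: "Event type (category below); diagnosis codes selected from Mayo Clinic database of ICD codes". Chart review then verifies the codes. No follow-up window is stated.
- **Trial primary endpoint (Design Overview).** "The primary safety endpoint will be a composite of post-dismissal cardiac death/spontaneous MI <30 days or stent thrombosis <90 days of discharge".
- **Trial secondary endpoints (Design Overview; also Specific Aim 2 and Aim 2: Detailed Approach).** "post-dismissal assessment for BARC 3 or 5 bleeding, all-cause death, any MI, and/or repeat revascularization up to 180 days", plus other BARC bleeding.
- **Definitions (item 5).** Cardiac death, spontaneous and periprocedural MI, stent thrombosis and BARC bleeding are defined. Ischemic stroke and TIA are not.
- **Ascertainment.** Item 6d has the coordinator "inquire about ischemic symptoms, readmissions at other hospitals with MI, or any bleeding". Item 6c covers the same day-30 and day-90 calls and asks about readmission without limiting it to MI. Item 3 sends hospitalizations to the adjudication committee and restricts the analysis to study-related events that the committee confirms.
- **Population (Table 1).** Prior ischemic stroke is a qualifying criterion. The minor form reads "Any ischemic stroke at any time not meeting the major criterion".

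**The concern.** The study is single-arm, so the registry cohort is the only DAPT comparison group it describes. Specific Aim 1 speaks of noninferiority for ischemic events, and the Aim 2 research design hopes to associate the regimen with fewer bleeding and ischemic events. Neither statement can be supported if an ischemic event means one thing in the trial and another in the controls.

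The second issue is safety reporting. The plan stops aspirin in every participant, within a population that can qualify partly through prior ischemic stroke. The plan treats stroke as relevant elsewhere: a stroke disqualifies a PCI from being called successful, and the introduction cites a one-month DAPT trial in HBR patients that was judged partly on cerebral ischemic events. Yet a participant who survives an ischemic stroke after enrolment adds nothing to any listed endpoint.

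**Working it through.** The plan states no margin, alpha, power or comparator rate for this comparison, so it has no figure to reproduce. The check sets the lists side by side and then asks which way the mismatch could push.

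**Step 1. Component lists.**

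| Component | Trial primary | Trial secondary | Control cohort |
|---|---|---|---|
| Cardiac death | <30 days | within all-cause death | not listed |
| All-cause death | no | yes | not listed |
| MI | spontaneous, <30 days | any, to 180 days | yes, no window |
| Stent thrombosis | <90 days | not listed | not listed |
| Repeat revascularization | no | yes | not listed |
| Non-fatal ischemic stroke/TIA | no | no | yes, no window |

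MI is the only shared component. Each side has at least one component that the other lacks. A fatal stroke would enter the trial only as a death.

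**Step 2. Net effect of the definitions.** Let S be the percentage of patients whose only event is ischemic stroke/TIA. Let D be the percentage whose only event is cardiac death or stent thrombosis without MI. With the same true risks in both cohorts and a common window:

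- control rate = MI + S
- trial rate under the primary composite = MI + D
- control minus trial = S - D, because MI cancels

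The documents give neither S nor D. Assumed ranges are 0.3% to 2% for S and 0.5% to 3% for D.

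| S | D | S - D (points) |
|---|---|---|
| 0.3% | 3% | -2.7 |
| 0.5% | 1.5% | -1.0 |
| 1% | 1.5% | -0.5 |
| 0.5% | 0.5% | 0 |
| 1% | 0.5% | +0.5 |
| 2% | 0.5% | +1.5 |

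The sign changes within plausible values. If all-cause death or revascularization were pooled on the trial side, D would grow and S - D would fall further.

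**Step 3. Scale.** Table 2 gives death or MI at 30 days as 9% overall and 5% in 2017. The unweighted mean of its yearly 30-day values is 72/8 = 9.0%, which agrees with the stated total. Against 5%, the two extremes are 1.5/5 = 30% and 2.7/5 = 54%. Against 9% they are 1.5/9 = 17% and 2.7/9 = 30%. Table 2 itself counts death or MI, which is a third definition, so it serves only for scale.

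**Step 4. Would a stroke/TIA be seen at all in a trial this small?** The chance of at least one event in n patients is 1 - (1 - S)^n.

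| S | n = 100 | n = 150 |
|---|---|---|
| 0.3% | 26% | 36% |
| 0.5% | 39% | 53% |
| 1% | 63% | 78% |
| 2% | 87% | 95% |

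If stroke/TIA were an endpoint and none occurred in 100 patients, the one-sided 95% upper limit would be 1 - 0.05^(1/100) = 3.0%. As the plan stands, the endpoint results could not make even that statement.

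**The case against.** A reader might infer that counting stroke/TIA only among controls inflates the control rate and so favours the trial regimen. The documents do not support this. The inference compares MI plus stroke/TIA in controls with MI alone in the trial, which sets the trial's own cardiac deaths and stent thromboses to zero. Item 5 also classifies deaths as cardiac unless another cause is clear, which raises the trial's count.

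A reader might also infer that cerebral ischemia would go unrecorded. That too is more than the text shows. Item 6c asks about any readmission, the calls ask about ischemic symptoms, and hospitalizations go to adjudication. The Aim 2 section on potential problems describes retrieving outside records. Its adverse-event list names hemorrhagic stroke and then breaks off in the supplied text, so ischemic stroke cannot be called absent from safety monitoring.

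Two further objections are fair:

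- Control events are recorded by category, so an MI-with-MI comparison remains possible, and no rule requires pooling MI with stroke/TIA.
- The controls are meant to be HBR patients too, so prior stroke does not by itself tilt the comparison.

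These objections remove any claim about direction or about missed ascertainment. They do not supply a common definition. No rule says which categories are to be compared or over what window, and hearing of a stroke does not place it in an endpoint.

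**Conclusion.** The point holds as a mismatch in both directions. The control list has ischemic stroke/TIA, which the trial's endpoints lack. The trial's endpoints have death, stent thrombosis and repeat revascularization, which the control list lacks. The ischemic rates are not comparable as written, and the sign of the bias is unknown. Over the assumed ranges the definitions alone contribute -2.7 to +1.5 points. That range rests on assumed values of S and D, equal true risks and a common window.

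Separately, and without any assumption about rates, a non-fatal ischemic stroke or TIA after aspirin is stopped cannot enter the trial's endpoint results, even if it is captured as a hospitalization or adverse event. This is worth correcting because it limits what the study's only DAPT comparison can conclude.

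**What to change.** 1. Add ischemic stroke/TIA to Aim 2 as an adjudicated secondary endpoint, with a definition in item 5 alongside the others.
2. State that the cohorts will be compared only on matched components over the same time window: MI with MI (same type of MI), and MI + stroke/TIA with MI + stroke/TIA.
3. Compare the primary composite with controls only if death and stent thrombosis are also abstracted for controls during the chart review already planned. Otherwise report it for the trial alone.
4. Align the wording of 6d with the unrestricted readmission question in 6c.

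The cost is one endpoint line and definition, one reworded call question, a few more adjudication packets and some added abstraction for controls. The trial's reported ischemic rate may be slightly higher.
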